## 2. *Exploratory Outcomes*

Appetitive hormone analysis: Participants will have three blood draws per visit. For each visit, the first blood draw (fasting) will occur at the start of the visit prior to drug administration. Second blood draw will occur 180min after drug administration (and 30min after a fixed milkshake consumption). Third blood draw will occur 210min after drug administration (and 60min after a fixed milkshake consumption). Blood samples for satiety hormones will be assayed using Bio-Plex Pro Human Diabetes 7-plex Assay (Bio-rad, Hercules, CA). This kit analyzes adiponectin, amylin, and GLP-1. Additionally, a custom Human Cancer Panel 1 with only prolactin will be used to analyze prolactin concentrations (Bio-rad, Hercules, CA) using a Millipore Luminex (Darmstadt, Germany). Using the 3 timepoints for the blood draws, we will create the area under the curve (AUC) for each appetitive hormone (prolactin, adiponectin, amylin, GLP-1, insulin) for each visit. AUC values will be entered into 2x2 repeated measures mixed models including drug-by-gene interactions. Control variables of no interest to be included are BMI, gender, visit number, and baseline (fasting) hormone levels.

Behavioral response inhibition analysis: Reaction time, % commission errors and % omission errors from the Stop Signal Task will be used as a behavioral measure of inhibition. The three outcome variables will be entered into 2x2 repeated measures mixed models including drug-by-gene interactions. Control variables of no interest to be included are BMI, gender, visit number, and pre-task nausea ratings.

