#### B. Study Objectives

**Aim 1**: To test the hypothesis that acute bromocriptine administration will alter neural and perceptual hedonic drivers of eating behavior (Visual analog scales), both contributing to a decrease in palatable food intake in those at high risk for T2DM. We expect that bromocriptine will increase BOLD response during palatable food intake in dopaminergic brain regions thought to encode reward and increase perceptual hedonic food ratings. We also expect that bromocriptine will result in decreased ad lib palatable food intake.

**Aim 2**: Test whether the A1 variant of the DRD2 TaqIA polymorphism, which is associated with reduced dopamine-D2 receptor density and dopamine signaling, moderates the impact of bromocriptine on neural and perceptual hedonic drivers of eating behavior. By testing the bromocriptine by TaqIA allele status interaction, we expect that the effects described in aim 1 will be pronounced in those with at least 1 A1 variant of the TaqIA polymorphism.

Exploratory Aim 1: To test the hypothesis that acute bromocriptine administration will alter the homeostatic mechanisms of satiation (meal termination). We expect bromocriptine to modify endocrine-mediated satiation signaling via suppressed prolactin, augmented adiponectin, amylin, glucagon like peptide-1 (GLP1), and decrease postprandial plasma glucose and insulin.

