# C. Study Design

This within-subject pilot study will look at 180 overweight/obese (25 < BMI < 35) adults ages 18-35 years of age. All participants will be screened at the first visit for 50 eligible participants who will complete the other visits. 25 participants will have the DRD2 TaqIA A1 allele and 25 will have the A2/A2 variant. The study will be completed over two testing visits with a two-week washout period in between. Following published reports of the effect of acute administration of bromocriptine (10), participants will be given a 1.6mg dose of either bromocriptine-QR (Cycloset) or a placebo after a 6-8 hour fast, paralleling the recommended dosage and time of administration (11). Order of agonist/placebo will be counterbalanced across the two visits. At both visits, the participant will have a fasting blood draw, anthropometric measurements, complete visual analogue scales (VAS) for hunger, and satiety and surveys. Once bromocriptine/placebo is metabolically active (~60 mins) subjects will undergo a functional MRI with our milkshake receipt paradigm and a resting state MRI to assess functional connectivity. The Biomedical Research Imaging Center (BRIC) is located on the UNC-CH campus and 7-10 min walk from our laboratory (Neuropsychology of Ingestive Behavior Laboratory). Post-MRI, subjects will consume a fixed portion of milkshake (12 fl oz) and perform VAS hedonic ratings; will complete a test of reaction time and behavioral impulsivity, and two postprandial blood draws (30 & 60mins post milkshake ingestion). Finally, subjects will perform perceptual hedonic assessments of palatable foods and given the opportunity for ad lib consumption.

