# 2. Testing Visits - Outline

At the Neuropsychology of Ingestive Behavior Lab

Baseline: Fasting blood draw, fasting drug or placebo administration

Baseline-60 minutes: Visual analogues scales (VAS) hunger and satiety, height and weight measurement, demographic and psychological surveys, waiting for drug to become active 60 minutes: Walk to Biomedical Research Imaging Center

At the Biomedical Research Imaging Center

90 minutes - 150 minutes: VAS hunger and satiety, MRI assessment, taste administration, resting state, anatomical scans

At the Neuropsychology of Ingestive Behavior Lab

150 minutes-180 minutes: VAS hunger and satiety, fixed milkshake consumption

180 minutes: Blood draw

180 minutes-210 minutes: Behavioral impulsivity, surveys

210 minutes: Blood draw

210-240 minutes: VAS ratings, hedonic ratings, ad libitum food intake

The testing visit will last approximately 4 hours. Testing visit occurs twice for each participant.

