### **B. Analysis Plan**

#### *1. Primary and Secondary Outcomes*

Behavioral data analysis (food intake + hedonic ratings of food). Continuous variables will be summarized by descriptive statistics (e.g., mean, SD, range, median), examined via graphical analyses (e.g. histogram, Q-Q plot) and analyzed to assess the normality of the data. Data transformation of continuous variables will be used as necessary. Model assumptions and potential outliers will be analyzed with various modeling diagnostics and plotting techniques. Visual analog scale (VAS) measures will be analyzed using PROC MIXED implemented in SAS (Version 9.4, Cary, NC). VAS scales for milkshake, snack food pleasure and desire, ad lib intake of those foods as well as changes in hunger (fasted to fed) will be entered into 2x2 repeated measures mixed models including drug-by-gene interactions which addresses Aim 1a and Aim 2. Control variables of no interest to be included are BMI, gender, visit number and nausea (after scan assessments only). In addition to main effects of the drug and the TaqIA allele status, interactions with  $p < 0.10$  will be probed with least squared mean comparisons of a priori contrasts of interest including tests of the: 1) impact of TaqIA allele status with bromocriptine, 2) impact of TaqIA allele status without bromocriptine 3) impact of bromocriptine on those with the TaqIA A2/A2 variant, and 4) impact of bromocriptine on those with at least one TaqIA A1 variant.

fMRI data preprocessing: Neuroimaging data will be preprocessed using the fMRIPrep pipeline [45]. DICOMS will be converted to the Brain Imaging Data Structure (BIDS file structure) [46], then preprocessed using fMRIPrep. fMRIPrep preprocessing includes skull stripping using Advanced Normalization Tools (ANTs); susceptibility distortion correction using field maps; tissue segmentation using FSL's Automated Segmentation Tool (FAST); and spatial

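### Does the exploratory hormone AUC need a stated integration rule and time origin before it can be analysed soundly?

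*SAP*

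**What the plan says.** SAP B.2 (Appetitive hormone analysis) takes three draws per visit. The first is a fasting draw at the start of the visit, before dosing. The other two are described as "Second blood draw will occur 180min after drug administration (and 30min after a fixed milkshake consumption") and "Third blood draw will occur 210min after drug administration (and 60min after a fixed milkshake consumption"). From these, "Using the 3 timepoints for the blood draws, we will create the area under the curve (AUC) for each appetitive hormone", one area per hormone per visit. The areas enter 2x2 repeated measures mixed models with a drug-by-gene interaction. The covariates are BMI, gender, "visit number, and baseline (fasting) hormone levels".

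Protocol F.2 lists the fasting draw together with dosing, at baseline. Exploratory Aim 1 in Protocol B expects changes "via suppressed prolactin, augmented adiponectin, amylin, glucagon like peptide-1 (GLP1), and decrease postprandial plasma glucose and insulin". Neither document names an integration rule, chooses between total and incremental area, or says from which moment the AUC clock runs.

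**The concern.** The post-milkshake draws are timed on two clocks, from the drug and from the milkshake, and the fasting draw has no minute value on either. One analyst could integrate over 0, 180 and 210 minutes. Another could treat the fasting sample as the value at the start of the meal and integrate over 0, 30 and 60. The two weight the post-milkshake draws very differently, so the same samples could give different areas and sometimes different verdicts, and the version could be picked after seeing the data.

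The gap between dosing and the milkshake adds to the worry. It runs 150 minutes without a sample, although the Protocol expects an active drug well within it ("Once bromocriptine/placebo is metabolically active (~60 mins) subjects will undergo a functional MRI") and gives milkshake tastes in the scanner during it ("90 minutes - 150 minutes: VAS hunger and satiety, MRI assessment, taste administration, resting state, anatomical scans"). Any AUC rule must assume something about that interval.

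**Working it through.** **Inputs.** Draw times are from SAP B.2. The fasting draw is taken as minute 0, because Protocol F.2 lists it with dosing (assumption). The documents give no AUC figure to reproduce and no correlation between draws. For the two post-milkshake draws, adjusted for fasting level, I assume equal variances and a correlation r of 0.3, 0.5 or 0.7.

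**1. Do the clocks agree?** 180 − 30 = 150 and 210 − 60 = 150. Both put the milkshake at 150 minutes, where Protocol F.2 starts the milkshake window. This is one schedule described twice.

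**2. Trapezoid weights.** Each draw's weight is half the sum of its adjacent intervals.

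| Placement (min) | Fasting | 30-min draw | 60-min draw | Ratio of last two |
|---|---|---|---|---|
| 0 / 180 / 210 | 180/2 = 90 | (180+30)/2 = 105 | 30/2 = 15 | 7:1 |
| −150 / 30 / 60 | 90 | 105 | 15 | 7:1 |
| 0 / 30 / 60 | 15 | 30 | 15 | 2:1 |
| Fasting carried flat to 150 | 75 + 90 = 165 | 30 | 15 | 2:1 |

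The label on the clock does not matter. Only moving the fasting value away from its own time changes the ratio. If the fasting draw is 15 or 30 minutes before dosing, the first ratio becomes 112.5:15 = 7.5:1 or 120:15 = 8:1.

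**3. Total or incremental?** The net incremental area equals the total area minus fasting level × duration. With that visit's fasting level as a covariate, any multiple of it is absorbed by its coefficient, and the drug and drug-by-gene terms do not move. A simulated data set of 42 subjects confirmed this: the drug t was 1.2271 for both forms at 0/180/210 and 1.3380 for both at 0/30/60. This choice therefore makes no difference on untransformed values. What remains is 7:1 against 2:1.

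**4. How far apart are the two versions?** With weights (7, 1) and (2, 1), the correlation is (15 + 9r) / √[(50 + 14r)(5 + 4r)]. At r = 0.5 this is 19.5 / √(57 × 7) = 0.976.

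| | r = 0.3 | r = 0.5 | r = 0.7 |
|---|---|---|---|
| Correlation of the two versions | 0.966 | 0.976 | 0.986 |
| False-positive rate, better of two reported (nominal 5%) | 6.2% | 6.0% | 5.8% |
| Power, equal effect at both draws: 7:1 | 69% | 73% | 76% |
| Power, equal effect at both draws: 2:1 | 78% | 79% | 79% |
| Trials where the verdicts differ | 10% | 7% | 5% |

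The false-positive row is 1 − P(|Z₁| < 1.96, |Z₂| < 1.96) for a bivariate normal pair. Power is for an effect that the simple mean of the two draws detects with 80% power. The last row is for the same equal effect.

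**5. Size of the reported effect.** An effect d at both draws adds 105d + 15d = 120d to the first area and 30d + 15d = 45d to the second. Most of that contrast is the length of the window: 120d/210 = 0.57d per minute against 45d/60 = 0.75d per minute. In standard-deviation units the 2:1 version is larger by √[(50 + 14r)/64] / √[(5 + 4r)/9] = 1.11, 1.07 and 1.04 at the three values of r.

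**The case for a change.** The best case for a change is that the scheduled-time reading, though literal, has a cost. It gives the 60-minute draw 15/120, one eighth of the post-milkshake weight, while Protocol G (Blood Draws) justifies the pair of draws as together covering the GLP1 peak. An analyst with that purpose in mind might start the area at the meal. If the drug acted at 60 minutes only, power would be 9–10% under 7:1 and 44–46% under 2:1. With opposite effects, say −1 unit at 30 minutes and +3 at 60, even the sign changes: (105 × −1 + 15 × 3)/210 = −0.29 against (30 × −1 + 15 × 3)/60 = +0.25.

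The arithmetic stands, but it needs unusual patterns. An effect absent at 180 minutes and full at 210 is extreme. On the 6-hour half-life in Protocol H, drug level falls only about 6% between the draws (1 − 2^(−30/360)). That does not settle the hormone response, but it gives no reason to expect so abrupt a change. If the effect is at 30 minutes only, both versions do well: 99% or more under 7:1 and 95–96% under 2:1. The documents predict no pattern, so neither weighting can be called the better one.

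Two further points carry less weight. Logging the area would break the equivalence in step 3, and a net incremental area at or below zero cannot be logged. But "Data transformation of continuous variables will be used as necessary" stands in SAP B.1 under the behavioural data, and B.2 mentions no transformation of hormone areas. The unsampled 150 minutes do limit interpretation: no area built from these draws separates a meal response from a drug effect already present before the meal. That is a feature of the sampling design, and wording about the AUC would not alter it.

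**Conclusion.** No change is needed. The omission is real but narrow: the rule, the total-or-incremental choice and the time origin are unstated, while the position of every draw in the visit is stated. An analyst who follows SAP B.2 literally uses a trapezoid at about 0, 180 and 210 minutes with the visit's fasting level as covariate, and gets a valid test. The alternative placement is also valid if fixed in advance.

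The two versions correlate 0.966–0.986, disagree in 5–10% of trials when the effect is equal at both draws, and leave room for at most about one percentage point of false-positive inflation. Writing the rule down would be tidy, but it would not make the result sounder.

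This rests on a visit-specific fasting covariate, untransformed areas, equal variances at the two draws, and a correlation of 0.3 to 0.7 between them. It concerns exploratory outcomes only; the intake, rating and imaging analyses are unaffected.
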